11.3.1 Assessment of Adverse Events

Initial assessment of AEs must be made by the Principal Investigator using the relevant safety reporting form. The outcome of this assessment should be forwarded to the Sponsor for Sponsor review **within 48 hours** of the AE being detected by the research team. If the AE is determined to be serious, it must then be reviewed by the CI.

Each AE must be assessed for seriousness, causality and expectedness. Where the PI and Sponsor's reviews do not concur, the AE must be followed up as the more serious event.

11.3.2 Assessment of Seriousness

The assessor (PI / CI / Sponsor) should make an assessment of seriousness in the following manner:

11.3.2.1 Assessment of Expectedness

The assessor must consult the current version of the protocol to determine whether an event is expected or unexpected. Events that are anticipated (or 'expected') are listed below. An unanticipated (or unexpected) effect is anything not listed in the protocol.

Anticipated (Expected) Events:

Code	Event	Frequency
01	Breathlessness/intolerance to mask	High
02	Apnoeas/cessation of breathing	High
03	Hypopneas/shallow breathing	High
04	Snoring	High
05	Restlessness/poor sleep	High
06	Snoring	High
07	Irregular breathing	High
08	Any other event directly related to diagnosis of suspected sleep apnoea	High
09	Any other event directly related to the participant's existing medical conditions	High

If the event is classified as an anticipated effect (i.e. expected), which by its nature, incidence severity or outcome has been previously identified in the Protocol, then the event does not require reporting to the Regulatory Agencies (MHRA and REC) but must be recorded in the medical records and the relevant safety reporting form. The sponsor must be informed of this event **within 48 hours** of becoming aware of the event. This document must be retained with the CRF.

Where an event could be related to the medical device and is unanticipated, in relation to the protocol (i.e. a USADE or unexpected SAE), the PI must report this event to the Sponsor **within 24 hours** of becoming aware of the event. The Sponsor will report this event to both the Manufacturer and to the Regulatory Agencies within the required timelines.

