5.2 Previous studies

The Apne-Scan DC1 device is newly developed and has been accredited as a UKCA and CE Class 1 data collector device. Prototypes and development versions of the device have been tested both in the laboratory and overnight by people involved with its development. During these tests it was found to be safe and comfortable. It also recognised cessation of breathing (in effect, an apnoeic event) and shallow breathing (a hypopnea), delivering both the reduction in signal from the sensor during the event and also the duration of the event.

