11.1.5 Unanticipated Serious Adverse Device Effects (USADE)

A serious adverse device effect which by its nature, incidence, severity or outcome has not been identified in the current risk assessment.

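### The anticipated-events list in 11.3.2.1 lets some serious device-related events be classed as expected and exempt from MHRA and REC reporting, which conflicts with 11.1.4, 11.1.5, 11.3 and 11.4.3

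*Combined protocol and SAP*

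**What the plan says.** Section 11.3.2.1 tells the assessor to consult the protocol and gives a default: "An unanticipated (or unexpected) effect is anything not listed in the protocol". The list that follows has three columns (code, event, frequency) and nine coded rows.

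- Row 01 is "Breathlessness/intolerance to mask".
- Rows 02 and 03 are "Apnoeas/cessation of breathing" and "Hypopneas/shallow breathing".
- Rows 04 and 06 are both snoring. Rows 05 and 07 are poor sleep and irregular breathing.
- Row 08 is "Any other event directly related to diagnosis of suspected sleep apnoea".
- Row 09 is "Any other event directly related to the participant's existing medical conditions".

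The frequency is High in every row. An event that matches the list need not go to the MHRA or the REC. It must still be recorded, and the Sponsor told within 48 hours. A possibly device-related event that is unanticipated against the protocol goes to the Sponsor within 24 hours, and the Sponsor then informs the manufacturer and the regulators.

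The definitions use a different reference. Section 11.1.5 calls a serious device effect unanticipated if it "has not been identified in the current risk assessment", and section 11.1.4 is its mirror image.

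**The concern.** An expectedness list should let an assessor tell a known, tolerable effect from a new or worse one. This list names kinds of event only. It gives no severity to compare an event with, and its frequency column does not distinguish one row from another. Rows 08 and 09 describe what an event is related to, which is a causality judgement, although section 11.3.1 asks for causality and expectedness as separate assessments.

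At stake is whether a serious harm with a device contribution reaches the REC and the MHRA. The doubtful cases are those of mixed cause, where the device and the participant's disease may both have contributed. These are also the cases in which device harm is hardest to recognise.

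**Working it through.** No formula or sample-size figure is involved. The check is a count of the list, two illustrative events run through the rules, and a comparison of sections.

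**1. Count of the list (11.3.2.1)**

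| Feature | Rows | Count |
|---|---|---|
| Frequency High | 01–09 | 9 of 9 |
| Severity or seriousness limit | none | 0 of 9 |
| Open-ended, no event named | 08, 09 | 2 of 9 |
| Events the device is meant to detect | 02, 03 | 2 of 9 |
| Names a mask effect | 01 | 1 of 9 |
| Duplicate | 04 = 06 | 9 − 1 = 8 distinct rows |

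**2. What counts as a match.** The rule lists nature, incidence, severity and outcome as alternatives joined by *or*. The table states no severity or outcome, so an event can match by its nature alone.

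**3. Event A: serious breathlessness caused by the mask, leading to admission.** It is serious under 11.1.3 and device-related under 11.1.2 and 11.1.6. Its nature is in row 01, so under 11.3.2.1 it is expected and exempt from MHRA and REC reporting.

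**4. Event B: a cardiac event in a participant with known heart disease, partly due to the device.** Section 11.1.6 counts an event attributable in part to the device as a serious adverse device effect. If it is also directly related to the heart disease, it fits row 09. It is then a serious device effect and also expected and exempt.

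**5. The same events under other sections**

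| Section | Treatment of events A and B |
|---|---|
| 11.3.2.1 | Expected; no MHRA or REC report |
| 11.3 | If the CI considers the event related, to the Sponsor and REC within 7 days; expectedness is not a condition |
| 11.4.3, REC | Related serious events are reportable; unanticipated ones are a separate bullet, so the first bullet does not depend on expectedness |
| 11.4.3, MHRA | Device-related events with a CE/UKCA marked device are reportable; no expectedness test |

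The REC conflict is direct. The MHRA sentence is framed around intended use of a marked device in a post-market setting. The conflict there assumes that it is meant to cover this study, and its inclusion in the protocol suggests that it is.

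**6. Reference document.** Sections 11.1.4 and 11.1.5 use the risk assessment. Section 11.3.2.1 and the REC paragraph of 11.4.3 use the protocol list. An event on the list but absent from the risk assessment would be unanticipated under 11.1.5 and expected under 11.3.2.1.

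**The case against.** The strongest reply is that classification as expected does not hide an event.

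- The PI informs the Sponsor of all adverse events (11.2.3).
- Serious events go on the Trust incident system (11.4.3) and to the manufacturer within 24 hours (11.4.4).
- The Sponsor reviews the PI's assessment, and disagreement is resolved towards the more serious view (11.3.1, 11.4.2).
- Causality is graded separately on a five-level scale (11.3.2.2).

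All of this stands, so it would be wrong to infer that device harm cannot be separated from the disease. It does not remove the defect. The Sponsor's review is a safeguard only if it disagrees with the PI, and both are directed to the same list. The routes in 11.3 and 11.4.3 contradict the exemption, and nothing says which governs.

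A reader might also infer that almost any event is expected and the unanticipated category nearly empty. The text does not support that. Rows 08 and 09 both require a direct relation, so an unlisted harm from the device alone, such as skin injury or an electrical fault, stays unanticipated.

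Nor does listing rows 02 and 03 turn every recorded apnoea into an adverse event. Section 11.1.1 requires an untoward occurrence, and 11.3 restricts what is recorded. The protocol simply does not say how these recordings are to be treated.

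Finally, an assessor could argue that an unusually severe case of a listed event is unanticipated, because its severity is not identified. The *or* wording in 11.1.5 allows this reading, while the parallel wording in 11.1.4 and 11.3.2.1 allows the opposite one. That confirms that the boundary is unclear.

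**Conclusion.** The point holds in this form: a range of events, including serious device-related ones, can be classed as expected under a stated rule and exempted from regulatory and ethics reporting. That exemption contradicts 11.3 and 11.4.3, and the protocol names two different references for expectedness. It should be corrected, since it bears on safety classification and the remedy is cheap.

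The conclusion rests on reading the list as written and on events A and B as illustrations; the documents give no rate for either. The risk assessment is not among the documents, so whether it differs from the list in fact cannot be checked.

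Two further inferences should not be drawn.

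- **A share of the cohort.** Section 4.1 says that more than 25% of referrals are snorers. It is tempting to conclude that up to (1 − 0.25) × 25 = 18.75, about 18 of 25 participants, would have a listed event. But the section does not say that the remainder have apnoeas, and snorers themselves match rows 04 and 06. No percentage follows.
- **A contradiction with section 5.2.** That section says of earlier testing, "During these tests it was found to be safe and comfortable". The testers were people involved in developing the device, using prototypes and development versions. The list concerns clinic referrals wearing the mask together with a standard test. The two statements can both be true.

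**What to change.** 1. Remove rows 08 and 09, or replace them with named events. Delete the duplicate snoring row.
2. State that apnoeas, hypopneas, snoring and irregular breathing recorded by the tests are outcome data and not adverse events in themselves.
3. Limit the reporting exemption in 11.3.2.1 to non-serious events.
4. Name one reference document for expectedness and use it in 11.1.4, 11.1.5 and 11.3.2.1, with the REC paragraph of 11.4.3 aligned to it.
5. Reconcile 11.3.2.1 with 11.3 and 11.4.3, so that a site has one answer on whether a device-related serious event is reported when it is expected.

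The cost is a short amendment touching several safety sections. Under 14.2 it needs approval by the CI and the Sponsor, and REC review if it counts as substantial. A few more events may then need Sponsor or regulatory review, which should be a small load with 25 participants studied for one night each.

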11.3.2.2 Assessment of Causality

The assessor of any causality assessments will use clinical judgement to determine the relationship between the event and the medical device. The assessor must consult the current version of the Protocol. When making a causality assessment, the following definitions should be used:

Not Related	There is no evidence of causal relationship to the Investigational Device.
Unlikely	There is little evidence to suggest there is a causal relationship. There is another reasonable explanation for the event (e.g. the participant's clinical condition, other concomitant events or medication).
Possible	The relationship with the use of the investigational medical device is weak but cannot be ruled out completely

Probable	The relationship with the investigational medical device seems relevant and/or the event cannot reasonably be explained by another cause.
Causal Relationship	The serious event is associated with the investigational medical device beyond reasonable doubt.

11.4 Reporting Adverse Events

11.4.1 Reporting Adverse Events

The PIs assessment of seriousness, expectedness and causality of all AEs should be reported to the Sponsor **within 48 hours** of the research team becoming aware of the AE occurring. The Sponsor will then also undertake a review to ensure they agree with the PIs assessment of seriousness, expectedness and causality.

11.4.2 Reporting Non-Serious Adverse Events

If the PI reports to the Sponsor that the AE is non-serious, and the Sponsor agrees, there is no need to escalate further or report to regulatory bodies (REC / MHRA). All AE and ADEs must be observed to ensure that they do not escalate to an SAE/SADE. All AEs should be reported to the DMC and presented at the next TSC.

If the Sponsor does not agree with the PI's assessment, the AE must be treated as a more serious event and reported as described in section 11.5.3 below.

11.4.3 Reporting Serious Adverse Events

Reporting to Sponsor:

If the PI determines that the AE is serious, the relevant safety reporting form must be used to report all SAEs/SADEs/USADEs/ASADEs to the Sponsor. This form and any documents provided to the Sponsor in support of the SAE/SADE/USADE must be depersonalised (labelled with trial ID number) and must NOT contain any patient identifiable data.

The PI/research team at the site where the AE occurred must provide any additional information as required to complete the report. The PI/research team at site must actively following-up the affected participant(s) until either:

- The SAE/SADE/USADE resolves, or
- Until 30 days after the discontinuation of use of the medical device

Review and sign-off of SAEs:

The CI is responsible for the review and sign-off of all serious adverse events/effects. In the event that the CI is unable to sign the report immediately, the research team/site should not delay sending the report to the Sponsor. However, a CI signed copy must be forwarded to the Sponsor as soon as possible (and within 48 hours of the initial reporting).

Should the CI be unavailable, serious adverse events/effects can be signed off by [name].

Reporting to the MHRA:

Device related events involving a CE/UKCA marked device being used within its intended purpose/proof of concept studies in a post market surveillance study must be reported to the MHRA Adverse Incident Centre <https://aic.mhra.gov.uk/>. Reporting to the MHRA of such occurrences is undertaken by the Sponsor. Individual guidance on the reporting requirements for certain types of devices can be found on the MHRA website

<https://www.gov.uk/government/collections/medical-devices-guidance-for-manufacturers-on-vigilance>

Reporting to REC:

The following SAEs/SADEs are considered reportable to the REC that gave the favourable ethical opinion:

- Those related to the administration of the medical device or any of the research procedures.
- USADEs - i.e. unanticipated events not listed in the Protocol as an anticipated occurrence.

Reports to REC should be submitted, by the Sponsor, within 15 days of the CI becoming aware of the event using the Non-CTIMP Safety Report Form to the REC published on the HRA website <http://www.hra.nhs.uk/>.

The CI is also required to include a report of the safety of participants in the annual progress report to the REC.

Individual reports will be reviewed by the REC at a subcommittee or committee meeting. Any requests for further information should be provided as applicable and all correspondence should be copied to the Sponsor.

Reporting to NHS Trust:

SAEs, SADEs, USADEs or Device Deficiencies which occur at site must be reported on the Trust's electronic incident reporting system (e.g. Datix). Reporting of incidents must be carried out in accordance with the Trusts Incident and Accident reporting policy. All SAE/SADE/USADE reported to the Sponsor will be reviewed at the R&I COG and by the Director of R&I.

11.4.4 Follow-up of Adverse Events by Sponsor

Acknowledgement will be issued to the Investigator from the Sponsor via email within 7 days of receipt of a fully completed form, and this must be filed in the TMF/ISF.

Each SAE/SADE/USADE will be registered on the recognised Sponsor database and reviewed by the Sponsor or their delegate. This review may lead to queries being issued by the Sponsor/delegate to request signed documentation, clarify information or complete event outcome. All queries will be sent via email and must be responded to within the stated timeframe.

All SAEs and SADEs will be recorded on a SAE Form and will be reported within 24 hours of awareness to Apnea-Tech. This will be sent by email using the SAE Form to the company's Chief Technical Officer who is responsible for the medical device vigilance of this study.

Reports must be sent to:
Apnea-Tech's Chief Technical Officer

Copied to:
Sponsor's Clinical research Lead:

Apnea-Tech will notify the Competent Authority as soon as the Company becomes aware of any Medical Device Reportable (MDR) events.

11.5 Device Deficiencies

Inadequacy of a medical device with respect to its identity, quality, durability, reliability, usability, safety or performance.

Note: Device deficiencies include malfunctions, use errors, and inadequacy in the information supplied by the manufacturer including labelling.

All device deficiencies device shall be documented throughout the trial and reported on the relevant device deficiency form and retained with the CRF. The Sponsor shall take, where applicable, appropriate corrective and preventive actions to protect the safety of participants, users, and other persons.

Device deficiencies that did not lead to an adverse event but could have led to a serious adverse device effect will be reported as specified in section 11.3.2. if:

- a. suitable action had not been taken,

- b. intervention had not been made, or,
- c. circumstances had been less fortunate.

11.6 Quarantine of Devices

If a device is found to be defective or deficient then it should be withdrawn from the study and quarantined. If the device is off-site with a participant, it should be recalled using the contact information provided on the loan form and device accountability documentation.

If the device is assessed by the PI to be defective in a way which could have led to a Serious Adverse Device Event if used or usage had continued, then the MHRA must be contacted, by the Sponsor, within 1 week of the PI being made aware of the occurrence.

The device must not be returned to the manufacturer until the MHRA has been given the opportunity to carry out/complete an investigation. In addition, the device should not be:

- Discarded
- Repaired
- Returned to the manufacturer

All material evidence that may be required by the MHRA to undertake their investigation i.e. devices/parts that have been removed, replaced or withdrawn from use following an incident, instructions for use, records of use, repair and maintenance records, packaging materials, or other means of batch identification must be:

- Clearly identified and labelled
- Stored securely

This evidence should not be interfered with in any way, except for safety reasons or to prevent its loss. Where appropriate, a record should be made of all readings, settings and positions of switches, valves, dials, gauges and indicators, together with photographic evidence and eyewitness reports.

The Chief Investigator and the Sponsor will undertake any requirements outlined in the MHRA investigation and follow-up as instructed.

12. DATA HANDLING AND RECORD KEEPING

12.1 Data Handling

All data will be handled in accordance with the General Data Protection Regulations (GDPR), Apnea-Tech's SOPs and the participant's consent form. No data will be accessed for any patients who have not consented to be part of this study. Apnea-Tech or its analysis team at Keele University will not have any direct access to participant identities and participants' medical notes; participant information will be managed securely by the clinical research team.

12.2 Data Collection

Data collection will comprise of:

- The Baseline data, provided by the study team.
- The Participant Questionnaire.
- The recording of changes in flow downloaded from the participant's Apnea-Scan DC1.

12.3 Data Management, Quality, Security

- All study data will be held by participant number. Apnea-Tech will have no access to any patient identifiable information.

- Any Apne-Scan device not returned by post will be noted and the study team will have the option of confirming with the participant whether it was used and posted.
- Apnea-Tech will review the data provided and assess its completeness and quality. Any missing Baseline data will be requested from the study team. Missing or poor-quality participant-supplied data will be noted in the study data log.
- All data will be retained in a secure data repository for seven years.

13. DATA ANALYSIS

13.1 Analysis of Endpoints

13.1.1 Summary Statistics

The summary statistics produced from this exploratory study will be:

% participants successfully using the Apne-Scan DC1

Comparisons of primary diagnostic metric, AHI, between the standard sleep apnoea test device and Apne-Scan (based on recorded apnoeas and indicative hypopneas).

Primary Data Analysis

Comparison of primary diagnostic metric, AHI, between the standard sleep apnoea test device and Apne-Scan DC1.

Secondary Data Analysis

Comparison of primary diagnostic metric, AHI, segmented into mild, moderate and severe sleep apnoea, between the standard sleep apnoea test device and Apne-Scan DC1

Comparison of primary diagnostic metric, AHI, segmented into mild, moderate and severe hypopnoea, between the standard sleep apnoea test device and Apne-Scan DC1

Comparison of the participant's Apne-Scan data with their oxygen saturation levels from the standard test to identify the possibility of using the Apne-Scan data to predict the user's SPO2 level, possibly resulting in a first-generation algorithm, based on the Apne-Scan data, to predict the user's SPO2 level.

Analysis of the usability and effectiveness of the device in capturing the minimum data required for screening for sleep apnoea.

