1. LAY SUMMARY

1.1 Background

During sleep, many people have times when they breathe shallowly or completely stop. If a person stops breathing for more than 10 seconds, this is called an 'apnoea'. If shallow breathing, where the airflow drops by 30% or more, lasts for more than 10 seconds and results in the oxygen level in the person's blood decreasing by 3% or more, it is called a 'hypopnoea'. If a person has these events frequently, it disrupts their sleep and they do not awake refreshed. The tiredness can be so significant that it affects their life and can lead to accidents. These breathing events can also put strain on the heart, leading to cardiovascular conditions. These sleep disorders, usually called 'Sleep Apnoea', and can be treated for most people using 'continuous positive airways pressure', CPAP.

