4 BACKGROUND AND RATIONALE

4.1 Epidemiology

Sleep apnoea is a chronic condition where the person stops breathing for more than ten seconds (an apnoea) or shallow breathes for more than ten seconds (a hypopnea). Both events reduce the oxygenation of the blood. Less than 20% of sleep apnoea is caused by brain commands (central sleep apnoea) with more than 80% due to obstruction of the airways (obstructive sleep apnoea - OSA)¹.

OSA is a common, treatable condition. Recent research indicates that 936 million globally have mild-to-severe OSA, with 425 million with moderate-to-severe OSA¹. Even in first-world countries, the vast majority (up to 80%) of those affected remain undiagnosed and therefore untreated²⁻⁴. The lack of an appropriate level of case identification is driven by three factors: patients are frequently unaware of their own symptoms of sleep apnoea since they are often identified either by a bed partner or family member; clinicians in most medical specialties, and especially within primary care, do not have access to a simple sleep apnoea screening device; and health care professionals often lack the necessary training to identify high risk people and screen for early intervention. An accessible diagnostic technology and improved knowledge of the risk factors leading to sleep apnoea are therefore crucial to properly screen those with the highest risk.

1.5 million people in the UK have OSA. Up to 4 per cent of middle-aged men and 2 per cent of middle-aged women in the UK have OSA. It also affects 3 per cent of children in the general population; and as many as 50 per cent of children who are obese or have specific disabilities or other health conditions. Older people are even more at risk, with 15 to 20 per cent of those aged 70 and more estimated to have the condition. This means that OSA is the most common chronic respiratory condition, and the numbers affected are believed to be rising due to more people being overweight.⁴ Currently, due to the cost of the diagnostic equipment, OSA is diagnosed at specialist sleep clinics. More than 25% of the people referred to these centres are snorers, who could be screened out by Apne-Scan, releasing much needed specialist diagnostic capacity.

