10.3.2.3 Device Usage and Data Flow

The Apne-Scan DC1 device is a single user, single use device. It has a single flow sensor which records the pressure in the breath pathway twice per second. The definitions for diagnosing sleep apnoeas and hypopneas are all relative, based on percentage changes in sensor readings. The device will only recognise Indicative Hypopnea Events, because it does not confirm desaturation, unless the captured data can be used to accurately predict the user's SPO2 level at any time. There is no need for any calibration by the clinician or the user.

Once the device has been started, it continues to monitor the pressure in the breath pathway until the battery runs flat, which is targeted at over eight hours. The pressure readings are recorded sequentially on the internal memory for later download. They remain in the memory when the battery has run down.

After use the study participant return the used Apne-Scan DC1 and completed questionnaire, with the standard test, to the sleep clinic. The Apne-Scan data, together with the post-use questionnaire and the standard test's SPO2 level data, will be securely stored by participant number by the company and then analysed for possible apnoeas, indicative hypopneas and prediction artifacts within the Apne-Scan data of changes in SPO2 levels.

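### The primary AHI comparison sets an Apne-Scan index with no desaturation test against a reference index with no stated scoring rule, and neither has a defined denominator or a common time window

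*Combined protocol and SAP*

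**What the plan says.** Under Primary Data Analysis, section 13.1.1 compares AHI between the standard test and Apne-Scan. The summary statistics in the same section describe this as "Comparisons of primary diagnostic metric, AHI, between the standard sleep apnoea test device and Apne-Scan (based on recorded apnoeas and indicative hypopneas".

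On what an indicative event is, section 10.3.2.3 states: "The device will only recognise Indicative Hypopnea Events, because it does not confirm desaturation". It allows one exception, "unless the captured data can be used to accurately predict the user's SPO2 level at any time", which depends on an algorithm that the study is itself exploring.

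The protocol describes hypopnoea in two ways. Section 1.1 takes a drop in airflow of at least 30% for more than 10 seconds and adds an oxygen condition: the episode also "results in the oxygen level in the person's blood decreasing by 3% or more, it is called a 'hypopnoea". Section 4.1 describes someone who "shallow breathes for more than ten seconds (a hypopnea"; it says such events lower oxygenation but sets no threshold.

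On time, section 10.3.2.3 says of the device that "it continues to monitor the pressure in the breath pathway until the battery runs flat, which is targeted at over eight hours". Section 7.2.1 is concerned with breathing during sleep, but no section says how sleep or mask wear is to be identified.

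On data, section 12.2 lists three items: baseline data, the participant questionnaire and the Apne-Scan recording. Sections 10.3.1 and 10.3.2.3 also send the SPO2 data from the standard test for analysis, and 10.3.1 has the clinical team compare the outputs of the two devices.

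**The concern.** An AHI is a count of events divided by hours. For the difference between two AHIs to describe the sensor, both need the same counting rule and the same hours. Here the Apne-Scan counting rule is given and leaves out desaturation. The reference rule is not given, and neither are the hours for either device.

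Any difference will therefore mix three things: how well the pressure sensor detects reduced flow, how many flow reductions do not desaturate, and which hours were analysed. The study could not tell these apart afterwards. A good sensor could look biased, or offsetting distortions could pass for agreement. Section 9 says the results will inform a powered study, so a misattributed bias would carry forward into that design. The mixture also bears on the aim of identifying people without sleep apnoea (6.1) and on the safety hypothesis that moderate or severe disease is not missed (Synopsis).

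**Working it through.** **Figure to reproduce.** There is none. The documents give no expected AHI, bias, limit of agreement or power, and the 25 participants do not come from a calculation. The check is algebraic, and all numerical inputs are assumptions.

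**Inputs.**
- From the documents: the Apne-Scan numerator is apnoeas plus unconfirmed hypopnoeas (13.1.1, 10.3.2.3); a hypopnoea under 1.1 needs a fall of at least 3%; recording targets more than 8 hours (10.3.2.3).
- Assumed: h, the hypopnoea share of reference events; q, the share of indicative hypopnoeas without a 3% fall; T_ref and T_scan, the hours used as divisors. The reference is assumed to be scored as in 1.1, flow events to be detected alike by both devices, and any extra recorded time to contain no events (relaxed in step 4).

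**Formula.** Each confirmed hypopnoea corresponds to 1/(1 − q) flow-only events, so

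AHI_scan / AHI_ref = [(1 − h) + h/(1 − q)] × (T_ref / T_scan).

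**Step 1: numerator only.** Take a reference AHI of 15, made up of 5 apnoeas and 10 hypopnoeas per hour. Apne-Scan reads 5 + 10/(1 − q):

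| q | Apne-Scan AHI | Ratio to 15 |
|---|---|---|
| 0.2 | 17.5 | 1.17 |
| 0.3 | 19.3 | 1.29 |
| 0.4 | 21.7 | 1.44 |
| 0.5 | 25.0 | 1.67 |

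Over h from 0.3 to 0.7 and q from 0.1 to 0.5, the ratio runs from 1.03 to 1.70. It exceeds 1 whenever both h and q are above zero.

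**Step 2: denominator only (q = 0).** If Apne-Scan events were divided by 8 hours and reference events by fewer:
- 7 h: 15 × 7/8 = 13.1
- 6 h: 15 × 6/8 = 11.25
- 5 h: 15 × 5/8 = 9.4

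**Step 3: both together, 6 h against 8 h.** With the 5 + 10 split:
- q = 0.2: 17.5 × 0.75 = 13.1
- q = 1/3: (5 + 15) × 0.75 = 15.0, exact cancellation
- q = 0.5: 25.0 × 0.75 = 18.75

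The net sign depends on inputs that the documents do not give.

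**Step 4: events scored in the extra time.** Step 2 assumes that the 2 extra hours contribute nothing. If they contribute x events per hour, the index is (15 × 6 + 2x)/8. This equals 15 at x = 15 and is higher above that. Section 10.3.2.3 bases events on relative change and says nothing about off-face signal. If flat signal were scored as cessation of breathing, the time-base effect would be pushed upward, so even its direction is open.

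**Step 5: after the fix.** With one hypopnoea rule (q = 0) and one window (T_ref/T_scan = 1), the ratio is 1.00 for any h. What then remains is sensor performance.

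**The case against.** The strongest reply is that the numerator difference is disclosed and is part of the question. The device has no oximeter, the protocol calls its events indicative, and a screening comparison should use what the device delivers alone. This stands in part. The stand-alone comparison belongs in the plan and should stay. Disclosure, however, does not separate over-counting due to the missing oximeter from sensor error, and the plan has no analysis that does.

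The second reply is that recording length is not the divisor. Section 10.3.2.3 says how long the device runs, and the data could be trimmed to sleep or wear time. This stands: a denominator error is possible but not shown. The gap is that no rule is written.

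The third is that the 3% criterion is a lay-summary definition, not a stated rule for the reference devices, and that 4.1 gives no threshold. This also stands, and it makes the upward bias conditional.

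The fourth is that confirming Apne-Scan events with the SPO2 from the reference test makes the index test depend on its comparator, which can inflate agreement. This is correct and governs how such an index may be used.

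The last is that the study is exploratory, has 25 participants and takes data capture as its primary outcome, with the device comparison listed as a secondary outcome in 7.2.1. That lowers the weight of the point. It does not remove it, because 13.1.1 names the AHI comparison as the primary data analysis.

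**Conclusion.** The point holds in a limited form. The primary data analysis compares two indices without showing that they measure the same quantity. An upward bias in the Apne-Scan numerator is likely if the reference is scored as in 1.1. A time-base distortion is possible, in a direction that cannot be determined. The illustrations (15 becoming 17.5 to 25.0, or 11.25) rest wholly on the assumed event split, desaturation share and hours.

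Three stronger readings are not supported:
- A reader might infer that agreement is biased in two known and opposite directions. The documents give no divisor for either device, and off-face signal could act upward.
- A reader might infer that these shifts move patients between severity classes. The documents give no class cut-offs, so this cannot be checked.
- A reader might infer from 12.2 that the reference AHI is unavailable. Section 10.3.1 has the clinical team compare the outputs, so 12.2 is an incomplete list that conflicts with the data flow described elsewhere.

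This should be fixed, with moderate confidence. It is not critical to an exploratory study whose stated primary outcome is data capture.

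**What to change.** In 13.1.1:
- State the hypopnoea scoring rule and AHI denominator used for each reference device.
- Compute the indices of both devices over the same time-aligned window, limited to valid on-face signal, and recompute the reference AHI over that window.
- Keep (a), apnoeas plus all indicative hypopnoeas, as the stand-alone device result against reference AHI.
- Add (b), apnoeas plus only those indicative hypopnoeas followed by a fall of 3% or more in the reference SPO2. Label it a decomposition or sensitivity analysis that is not independent of the reference.
- Add a comparison of the apnoea index alone, which needs no desaturation rule.

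Record the start time of both devices. Section 10.3.2.3 says readings are stored in sequence and mentions no clock time, and 10.3.2.6 has the device dismantled after return, so alignment may be hard to recover later.

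In 12.2, list the reference AHI, apnoea and hypopnoea counts, analysed time and SPO2 trace, consistent with 10.3.1 and 10.3.2.3. Items beyond what 1.6 allows the company to receive can stay with the clinical team.

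The cost is wording, one recorded time per device, some alignment work and some recomputation by the clinical team. No new participant procedure is needed: the reference SPO2 is already supplied, and the planned SPO2-prediction analysis needs the same alignment. A written start time may allow only coarse matching of short events, which is a further reason to treat (b) as supportive.
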